8.3.7. Electrocardiograms

A 12-lead ECG will be performed during screening with the participant in a recumbent or semirecumbent position after 5 minutes of rest. The 12-lead ECG will be interpreted by the investigator at the site and will be used for immediate management. The decision to include or exclude a participant or withdraw a participant from the study based on an ECG flagged as "Abnormal, Clinically Significant" is the responsibility of the investigator, in consultation with the sponsor's medical monitor, as appropriate.

An additional ECG will be performed at the EOT visit.

Based on findings from a concentration-QTc analysis, a QT effect exceeding the threshold of concern (10 msec) can be excluded within the observed range of itacitinib plasma concentrations. Therefore, additional ECGs are not required and would only need to be performed at the investigator's discretion. Electrocardiograms that are identified as abnormal and clinically meaningful compared with the screening assessment should be reported as AEs.

8.3.8. Laboratory Assessments

Blood draws for laboratory assessments will occur at study visits indicated in Table 4. Table 21 summarizes the clinical laboratory analytes to be assessed. Blood draws will be completed before the participant receives study drug.

All laboratory assessments will be performed at a local (site) laboratory using institutional best practices. Results and normal reference ranges will be entered into the eCRF.

Table 21: Clinical Laboratory Analytes

Serum Chemistries	Hematology	Pregnancy Testing
Albumin ALP ALT AST Bicarbonate or CO ₂ (at screening and then as clinically indicated) Blood urea nitrogen or urea Calcium Chloride Creatinine Glucose Lactate dehydrogenase Phosphate Potassium Sodium Total bilirubin (Direct and indirect bilirubin required for participants with elevated total bilirubin). Total protein Total cholesterol	Complete blood count, including: Hemoglobin Hematocrit Platelet count Red blood cell count White blood cell count Differential count, including: Basophils Eosinophils Lymphocytes Monocytes Neutrophils	Female participants of childbearing potential only require a serum test at screening and EOT and a serum or urine pregnancy every 28 days. Pregnancy tests (serum or urine) should be repeated if required by local regulations.
Lipid Panel	Infection Screening Tests	
Triglycerides Cholesterol LDL HDL	HIV (if HIV status is unknown) Hepatitis B surface antigen Hepatitis B surface antibody Hepatitis B core antibody HCV antibody HBV-DNA (if required) HCV-RNA (if required) CMV-PCR and EBV-PCR	

Note: Additional tests may be required, as agreed upon by the investigator and sponsor, based on emerging safety data.

8.3.8.1. Hematology

Hematology assessments, including complete blood count with differential, will be performed at a local (site) laboratory using institutional best practices before administration of study drug. Results and normal reference ranges will be entered into the eCRF.

8.3.8.2. Serum Chemistry

All chemistry panel assessments will be performed at a local (site) laboratory from blood samples collected using institutional best practices before administration of study drug. For GVHD follow-up assessments on total bilirubin, ALT, and ALP will need to be reported. Direct

and indirect bilirubin are also required for participants with elevated total bilirubin. Results and normal reference ranges will be entered into the eCRF.

8.3.8.3. Pregnancy Testing

A serum pregnancy test will be required for all women of childbearing potential during screening and at the EOT visit.

Urine or serum pregnancy tests will be conducted locally every 28 days. If a urine pregnancy test is positive, results should be confirmed with a serum pregnancy test. If the serum pregnancy test is negative after a urine test was positive, the investigator will assess the potential benefit/risk to the participant and determine whether it is in the participant's best interest to resume study drug and continue participation in the study.

8.3.8.4. Hepatitis Screening

Participants with active HBV or HCV infection that requires treatment or who are at risk for HBV reactivation (ie, positive HBsAg serology) are excluded from the study. *Note:* Candidates with negative HBsAg and positive total HBc antibody may be included if HBV DNA is undetectable at the time of screening. Candidates positive for HCV antibody are eligible only if PCR is negative for HCV RNA.

Prior test results obtained as part of standard of care before allo-HCT confirming that a participant is immune and not at risk for reactivation (ie, hepatitis B surface antigen negative, surface antibody positive) may be used for purposes of eligibility, and tests do not need to be repeated. Participants with positive antigen serology results must have negative PCR results.

Participants whose immune status is unknown or uncertain must have results confirming immune status before enrollment.

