5.2. Exclusion Criteria

Participants are excluded from the study if any of the following criteria apply:

- 1. Has received more than 1 prior allo-HCT. Prior autologous HCT is allowed.
- 2. Has received more than 3 days/72 hours of systemic corticosteroid treatment for cGVHD.
- 3. Has received any other systemic treatment for cGVHD, including ECP. CNIs initiated before randomization may be continued at the same or lower dose; topical/inhaled steroids are acceptable.
- 4. Prior treatment with a JAK inhibitor within 8 weeks before randomization. Participants who received a JAK inhibitor for aGVHD are eligible only if they achieved CR or PR.
- 5. Removed in Amendment 6.
- 6. Presence of active uncontrolled bacterial, fungal, parasitic, or viral infection. Infections are considered controlled if appropriate therapy has been initiated and, at the time of screening, no signs of infection are present.
- 7. Active HBV or HCV infection that requires treatment, or at risk for HBV reactivation (ie, positive HBsAg). Participants with negative HBsAg and positive total HBc antibody may be included if HBV DNA is undetectable at the time of screening. Participants who are positive for HCV antibody are eligible only if PCR is negative for HCV RNA. Participants whose immune status is unknown or uncertain must have results confirming immune status before enrollment. Prior serology results are acceptable for determining eligibility.
- 8. Known HIV infection.
- 9. Evidence of relapsed primary hematologic disease, or receipt of treatment for relapse after the allo-HCT was performed, including DLIs for the treatment of molecular relapse.
- 10. Maintenance therapy for the primary hematologic disease started within 4 weeks before initiation of study treatment (Day 1) or plans to start maintenance therapy after Day 1.
- 11. Corticosteroid therapy at doses > 0.25 mg/kg per day methylprednisolone or equivalent for any treatment other than the diagnosis of cGVHD within 7 days of randomization.
- 12. Participants on mechanical ventilation or requiring oxygen support or FEV1 < 30%.
- 13. History or current diagnosis of cardiac disease indicating significant risk of safety for participation in the study, such as uncontrolled or significant cardiac disease, including any of the following:
 - a. Recent myocardial infarction (within 6 months before randomization).
 - b. New York Heart Association Class III or IV congestive heart failure.

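### Protocol 8.3.8.4 accepts two pre-transplant hepatitis B markers as proof of no reactivation risk without asking for a core antibody result

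*Protocol*

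**What the plan says.** Section 8.3.8.4 of the protocol has three parts that matter here.

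- The first paragraph excludes HBsAg-positive participants and adds in a Note: "Candidates with negative HBsAg and positive total HBc antibody may be included if HBV DNA is undetectable at the time of screening". Exclusion 7 in Section 5.2 carries the same condition: "Participants with negative HBsAg and positive total HBc antibody may be included if HBV DNA is undetectable at the time of screening".
- The second paragraph deals with reuse of standard-of-care results from before transplant. Results confirming that the participant is "immune and not at risk for reactivation (ie, hepatitis B surface antigen negative, surface antibody positive) may be used for purposes of eligibility" spare the site from repeating tests. The paragraph closes with "Participants with positive antigen serology results must have negative PCR results".
- The last paragraph says: "Participants whose immune status is unknown or uncertain must have results confirming immune status before enrollment".

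Four other places bear on the point. Exclusion 7 ends with "Prior serology results are acceptable for determining eligibility" and names no markers. The infection screening panel in Table 21 reads in part "Hepatitis B surface antigen Hepatitis B surface antibody Hepatitis B core antibody HCV antibody HBV-DNA (if required"), so the core antibody carries no condition while HBV DNA does. Section 8.1.2 allows routine results obtained before consent, with hepatitis serology as one of its examples, if they satisfy the protocol's criteria and fall within the study's timeframe. Section 8.3.5 refers sites to 8.3.8.4 for hepatitis B and C.

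**The concern.** The abbreviation ie turns the parenthesis in the second paragraph into a definition. Two markers are enough to be classed as immune and free of reactivation risk. The Note and exclusion 7 treat a third marker, the core antibody, as deciding whether an HBV DNA test is needed before entry. The reuse paragraph does not mention that third marker.

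What is at stake is an entry condition that the protocol itself sets for participant safety. If it is missed at entry, no later scheduled test would pick it up: Table 4 places hepatitis screening at the screening visit only, and Section 8.3.5 calls for further infection tests only on clinical suspicion. Liver chemistry is followed regularly and could raise that suspicion, but it is not a hepatitis B test. Section 5 also rules out eligibility waivers, so the criteria should read one way only.

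**Working it through.** No arithmetic applies. The check is to take candidates who are HBsAg negative and surface antibody positive before transplant, vary what is known of the core antibody, and see which rule governs.

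1. **Core antibody on file, negative.** The reuse paragraph applies, the HBV DNA condition does not. The texts agree.
2. **Core antibody on file, positive.** The Note and exclusion 7 apply on their own terms. The reuse paragraph waives repeat tests but says nothing that lifts the HBV DNA condition. No gap.
3. **Core antibody not on file, and the site draws it because Table 21 lists it.** The candidate moves to case 1 or case 2. No gap.
4. **Core antibody not on file, and the site relies on the reuse paragraph.** The two-marker definition is met. Nothing in that paragraph asks for the core antibody, so nothing triggers the HBV DNA test. If the core antibody is in truth positive, the entry condition goes unchecked.

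Only case 4 is a gap. The next question is whether any text forces case 4 into case 3.

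- *Table 21.* It points that way, since the drafters marked the conditional tests and left this one unmarked. It does not say that the reuse route still needs the full panel.
- *The waiver of repeat tests.* A test never done cannot be repeated, so the waiver need not reach the core antibody. This is a fair reading, but it is not stated.
- *Section 8.1.2.* It sends the site back to the protocol's criteria. It does not name markers, and 8.3.8.4 is the section that does.
- *The last paragraph of 8.3.8.4.* It applies when immune status is not established. The second paragraph has already declared the two-marker profile to be confirmed immunity, so a site following it sees nothing left to establish.
- *The last sentence of exclusion 7.* It accepts prior serology in general terms and adds no marker requirement.

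These texts narrow the gap. None of them expressly overrides the two-marker definition.

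The sentence on PCR does not help either. HBsAg is the only hepatitis antigen in Table 21, and exclusion 7 already shuts out anyone "at risk for HBV reactivation (ie, positive HBsAg"). The sentence therefore governs nobody who could otherwise enter, and it does not reach the core antibody.

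**The case against.** The best reply is that the protocol, read as a whole, already requires the test. Table 21 lists the core antibody unconditionally, Table 4 schedules hepatitis screening for everyone, the waiver speaks only of repeating tests, and Section 8.1.2 ties reuse to the protocol's own criteria. Permission to use certain results does not cancel a different listed test. This largely stands. A careful site would draw the missing core antibody, and many sites will have the result already. It does not settle the matter, because the specific eligibility rule, to which Section 8.3.5 directs sites, defines sufficiency by two markers and never says that a third is needed.

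Two stronger readings are tempting, and the documents do not support them.

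- A reader might infer that the protocol never asks for the core antibody, or that a candidate known to be core-antibody positive can enter without an HBV DNA test. Table 21 asks for it, and the Note and exclusion 7 act on a positive result.
- A reader might infer that the PCR sentence opens the door to an HBsAg-positive, PCR-negative candidate and so contradicts the exclusion. It states a necessary condition, not permission to enroll. Such a candidate stays excluded by the first sentence of 8.3.8.4 and by exclusion 7. The PCR sentence is redundant, not contradictory.

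**Conclusion.** The wording gap is real but minor. For harm to follow, three things must coincide: the core antibody was never measured, the site treats the reuse paragraph as sufficient despite Table 21, and the core antibody is in truth positive. The documents give no count of such candidates. The number is unknown and probably very small, and the count of places still to be randomized would not measure it.

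The conclusion rests on one assumption, that some site will read the two-marker definition as complete in itself. It needs no outside evidence on hepatitis B, because the mismatch lies between the protocol's own rules. It has no bearing on sample size, power, type I error or any endpoint. It is a point of participant safety and consistent eligibility, worth correcting when the text is next opened.

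**What to change.** In the second paragraph of 8.3.8.4, add a third element to the parenthesis: total core antibody negative. Candidates without a core antibody result then no longer meet the reuse rule on two markers. They have the test already listed in Table 21 and, if it is positive, the HBV DNA test the protocol already requires.

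Optionally, replace the redundant PCR sentence with one requiring undetectable HBV DNA at screening for participants whose total HBc antibody is positive. This repeats the Note, but puts the condition where a site relying on prior results will see it.

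Leave the last sentence of exclusion 7 alone. Tying it to 8.3.8.4 may look tidy, but that section describes reuse only of pre-transplant results showing hepatitis B immunity. The change could withdraw the broader permission exclusion 7 now gives, for example for prior HCV results or for hepatitis B results that do not show immunity.

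The cost is a short wording change, by amendment or clarification letter, and one extra core antibody test, plus HBV DNA if positive, for candidates with no result on file.

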8.3.8.5. HIV Screening

Participants with an active HIV infection are excluded from the study. Prior HIV screening results obtained as standard of care for allo-HCT confirming an HIV-negative status may be used for determining eligibility, and tests do not need to be repeated. Participants whose HIV status is unknown must have results confirming negative status before enrollment.

8.4. Pharmacokinetic Assessments

8.4.1. Blood Sample Collection

Pharmacokinetic samples will be obtained on Days 1, 7, and 28 for participants in Part 1 and Part 1 expansion (except Treatment Group D) as well as the first 70 participants randomized in Part 2. On each of these days, a predose blood sample will be drawn, study treatment will be administered, and serial blood samples will be taken at the intervals shown in Table 4 and Table 22.

After the first 70 participants are enrolled in Part 2, only a predose sample on Day 7 and 28 will be collected in subsequent participants (ie, participants 71-246).

The exact date and time of the PK blood draws will be recorded in the eCRF along with the date and time of the last dose of study drug preceding the blood draw (if applicable) and the time of

the most recent meal. Instructions for sample preparation and shipping will be provided in the Laboratory Manual. Participants will receive reminder cards in advance of the study visit providing instruction to hold the dose of study drug on the day of the visit, as well as a place to record the time of the prior dose of study drug and time of the most recent meal or snack consumed.

If PK samples are missing for a participant, PK sample collection should be performed at the next visit. On PK sample collection days, participants must refrain from taking study medication before arriving for the visit and should not have consumed any food within 8 hours before arriving at the clinic. A trough (predose) PK sample (30-minute window) should be drawn at each of the PK visits. Following the trough PK sample, the participant should take the assigned dose of study treatment, and subsequent timed samples will be taken if applicable. Food should be withheld until 1 hour after study drug administration.

Participants 71 through 246 in Part 2 of the study will have only predose samples collected on Day 7 and Day 28.

Table 22: Pharmacokinetic Sampling for Part 1, Part 1 Expansion, and Participants 1 Through 70 in Part 2

Study Day	Timing of Sample Relative to Itacitinib Administration					
Day 1	Predose	1 h ± 15 min	$2 h \pm 30 min$	$5 \text{ h} \pm 60 \text{ min}$		
Day 7	Predose	1 h ± 15 min	$2 h \pm 30 min$	$5 \text{ h} \pm 60 \text{ min}$		
Day 28	Predose	1 h ± 15 min	2 h ± 30 min	5 h ± 60 min		

8.4.2. Pharmacokinetic Analysis

Plasma samples will be analyzed for itacitinib by a validated liquid chromatography—tandem mass spectrometry assay. These samples will be analyzed by Incyte Corporation (Wilmington, DE) or its designee.

Pharmacokinetic parameters will be calculated from the plasma concentrations of itacitinib according to a model-independent approach or population PK approach. Instructions regarding sample collection, handling, and shipping will be provided in the Laboratory Manual.

The data will be used to validate the population PK model being developed across healthy volunteers and various patient populations including acute GVHD. If appropriate, the model will be used to generate individual post-hoc PK model parameters and calculate and/or simulate individual exposures. Observed PK parameters such as C_{min} (all participants) and C_{max} and T_{max} (data permitting) will also be presented and summarized. Exposure/response analyses may be performed using model-based AUCs or using observed trough values (C_{min}).

Data may also be used to further validate or refine PBPK and population PK models of itacitinib. These models may be used to aid in dose selection for Part 2 of the study.

8.6. Unscheduled Visits

Unscheduled visits may be performed at any time at the investigator's discretion, with appropriate clinical and laboratory measurements performed based on AEs or other findings. Data from these visits should be captured on the appropriate eCRF.

8.7. End of Treatment

When the participant permanently discontinues study drug, whether the participant is terminating the study treatment early or has completed the study treatment, the EOT visit should be conducted. If the EOT visit coincides with a regular study visit, the EOT evaluations will supersede those of that scheduled visit, and the data should be entered in the EOT visit in the eCRF. The participant should be encouraged to return for the safety follow-up visit.

8.8. Follow-Up

8.8.1. Safety Follow-Up

The safety follow-up period is the interval between the EOT visit and the scheduled safety follow-up visit, which should occur at least 30 days after the EOT visit (or after the last dose of study drug/treatment if the EOT visit was not performed). Adverse events and SAEs must be reported up until 1) at least 30 days after the last dose of study drug/treatment, the date of the follow-up visit, or the start of a new GVHD therapy or 2) until toxicities resolve, return to baseline, or are deemed irreversible, whichever is longer. Reasonable efforts should be made to have the participant return for the follow-up visit and report any AEs that may occur during this period. If the participant cannot return to the site for the safety follow-up visit, sites should attempt to contact the participant by telephone for assessment of AEs and SAEs. These contacts with the participant should be documented in medical records.

If a participant is scheduled to begin a new anti-GVHD therapy before the end of the 30 days safety follow-up period, the safety follow-up visit should be performed before treatment is started. Once new GVHD therapy has been initiated, the participant will move into the survival follow-up period.

8.8.2. Post-Treatment GVHD Follow-Up

Participants who complete itacitinib/placebo taper after an initial response (CR or PR) or discontinue early for reasons other than cGVHD progression and with no requirement for new

cGVHD therapy will be followed until cGVHD progression, initiation of a new cGVHD therapy, initiation of treatment for relapse/recurrence of the underlying hematologic disease, death, or end of study and for a maximum of 24 months from Day 1, at which point the participant may enter survival follow-up. The participant will be followed at clinic visits every 28 days (\pm 7 days) after the safety follow-up visit up to 1 year from Day 1 and then every 8 weeks (\pm 7 days) up to 2 years from Day 1.

8.8.3. Survival Follow-Up

Once a participant has completed the post-treatment GVHD follow-up (ie, 24 months from Day 1) or has confirmed GVHD progression or starts a new GVHD therapy, or experiences relapse/recurrence of the underlying hematologic disease, then the participant moves into the survival follow-up period and should be contacted by telephone, email, or visit at least every 8 weeks to assess for survival status until death or withdrawal of consent, whichever occurs first.

For participants having entered the survival follow-up period of the study, the site will use continuing participant records to supply data on subsequent treatment regimens, GVHD assessments (if discontinued treatment for a reason other than progression), and OS in the eCRF. For participants who do not intend to return to the study investigator for their ongoing care, follow-up should be maintained by phone contact, patient records, and public records/databases at intervals of no longer than 8 weeks.

8.9. Data Monitoring Committee

An external DMC will be formed to monitor the study. The DMC will consist of external experts in the field of allogeneic transplantation who will function autonomously from all other individuals associated with the conduct of the study, including investigators and sponsor personnel. The DMC will be responsible for reviewing results from the prespecified analysis and recommending an appropriate course of action based on these data. Details on the composition and responsibilities of the DMC can be found in the DMC charter.

9. ADVERSE EVENTS: DEFINITIONS AND PROCEDURES FOR RECORDING, EVALUATING, FOLLOW-UP, AND REPORTING

